**EFFECT OF 2-WEEK NIGHTLY MODERATE HYPOXIA ON GLUCOSE
TOLERANCE IN INDIVIDUALS WITH TYPE 2 DIABETES
(SLEEPDIABETES)**

NCT02513641

Document Upload Date: October 11, 2019

Latest IRB Approval Date: September 6, 2017

EFFECT OF 2-WEEK NIGHTLY MODERATE HYPOXIA ON GLUCOSE TOLERANCE IN INDIVIDUALS WITH TYPE 2 DIABETES (SLEEPDIABETES)

PI: [name]
Medical Investigator: [name].

BACKGROUND AND SIGNIFICANCE

Hypoxia in obese adipose tissue (AT) plays an important role in the development of whole-body insulin resistance by inducing local inflammation and the release of pro-inflammatory cytokines (reviewed in [1]). Detrimental effects of hypoxia are also evident in the altered glucose metabolism induced by sleep apnea, a condition characterized by intermittent and short hypoxic episodes [2, 3]. However, there are conflicting reports about the effects of altitude hypoxia on insulin action and glucose uptake [4].

Short-duration (4 hours) of exposure to moderate hypoxia has been shown to improve transient insulin sensitivity in type-2 diabetics [5], and more prolonged exposure was shown to increase whole-body glucose turnover and utilization in healthy subjects [6]. Exposure to hypoxic environments has also been shown to increase both whole-body glucose fluxes in healthy males and glucose uptake in human and murine skeletal muscle [7]. Controlled studies at altitude following acute exposure to hypoxia during exercise have reported improved carbohydrate metabolism, including increased glucose oxidation, reduced fasting insulin and glucose, and higher fluxes of glucose [8]. In addition, Cartee et al. reported enhanced insulin-independent translocation of glucose transporters by hypoxia during exercise [9]. Living at altitude in hypoxic conditions is associated with a lower prevalence of impaired fasting glucose and type 2 diabetes, as compared to low altitude [10].

Exposure to hypoxia has also been advocated as a possible therapeutic aid against obesity [11], hypoxia being known to reduce energy intake and to affect protein synthesis [12]. A highly publicized study showed reduced rates of obesity at high altitude [13]. Moreover, hypoxia has been shown to be beneficial as a complement to exercise in healthy non-obese [14], obese [15, 16] and athletes [17-19] to improve skeletal muscle function.

We have provided the first evidence that intermittent, nightly exposure to moderate hypoxia was beneficial in improving insulin sensitivity in healthy obese patients and, therefore, lowers the risk of developing type 2 diabetes [20]. Benefits included reduced fasting glucose levels and improved whole-body (skeletal muscle) and hepatic insulin sensitivity. *Whether such intermittent hypoxia improves glucose metabolism in people with type 2 diabetes is unknown.*

Reasons for the Protocol Modification and its Safety Implications:

The safety aspects and history of this protocol deserve further comment. It is important to the concept of using a hypoxia tent to treat diabetes to use as a home treatment. Although the degree of hypoxia generated by the tent was not a safety concern to the FDA, there was concern that safety would be compromised if the hypoxia of sleep apnea was added to the hypoxia of the tent. The initial approach to eliminating this safety concern in the study was to

PBRC# 2015-018

ensure that the participants did not have sleep apnea. Although this is one way to eliminate the threat of sleep apnea-associated hypoxia, it has been very hard to identify these individuals.

Another way to eliminate sleep apnea-associated hypoxia is to treat the sleep apnea with C-PAP, the standard way in which sleep apnea is treated. C-PAP is a continuous pressure administered by mask and adjusted to be sufficient to keep the airway open during sleep. The C-PAP essentially draws air from the surrounding environment and creates the pressure to keep the airway open using a fan. Therefore, the C-PAP machine could be put in the hypoxia tent with a cord extending to a wall socket outside the tent to power the machine. In this way the C-PAP would draw in hypoxic air from the tent, but would also insure that additional hypoxia would not occur due to the C-PAP eliminating the sleep apnea.

Since it has been shown by Foster GD et al. [24] that 86% of overweight and obese diabetic subjects have sleep apnea, we feel that, in addition to including subjects without sleep apnea, we should include patients with sleep apnea controlled on C-PAP. Both of these groups of patients will be protected from any additional hypoxia associated with sleep apnea that would add to the safe hypoxia generated by the tent, but including the group with sleep apnea controlled on C-PAP will allow us to enroll and complete the study which has only enrolled one patient in over a year when limiting those studied to those without sleep apnea.

HYPOTHESIS AND AIMS

Aim: To determine the effect of 2-week overnight sleep in moderate hypoxia on glucose tolerance in participants with type 2 diabetes.

Hypothesis: Exposure to moderate hypoxia (2400 m altitude) for 14 consecutive nights in obese, type 2 diabetic subjects will improve glucose tolerance

Primary endpoint: Results from the 75 g oral glucose tolerance test (OGTT) assessed by different statistical approaches including:

- Traditional area under the curve (glucose and insulin)
- Repeated measures mixed effect model
- Matsuda Index
- Kahn's calculation of indices of insulin sensitivity and insulin secretion

Exploratory endpoints: Fasting plasma fructosamine and hemoglobin A1-C as well as daily body weight

SUBJECTS

We plan to have n = 10 completers.

Inclusion criteria:

- Aged 20-65 yrs
- Have a BMI < 55 kg/m²
- Body weight 450 lbs or less

PBRC# 2015-018

- Have *either* been diagnosed with type 2 diabetes, or 125 mg/dl < Fasting Blood Sugar < 200 mg/dl, or hemoglobin A1-C \geq 6.5%
- Non-smokers
- Weight stable over the previous 3 months (< 3 kg fluctuation)
- Known diagnosis of sleep apnea and ownership of a continuous positive airway pressure (C-PAP) device that must be worn throughout the nights spent in the tent
- If no known presence of sleep apnea, be willing to spend one night in a sleep laboratory (Louisiana Sleep Foundation) to assess presence of sleep apnea

Exclusion criteria:

- Diagnosed with T2DM \geq 15 years ago
- Pregnant Women
- Current insulin treatment
- Treatment with sulfonylureas or glitinides
- Treatment with a GLP-1 agonist
- Any other diabetes medication other than an oral agent is exclusionary unless otherwise cleared by medical investigator.
- Chronic Obstructive Pulmonary Disease (COPD)
- Congestive heart failure
- Prior severe cardiovascular events such as stroke or myocardial infarction
- If treated for T2DM with other oral agent, no change in the treatment for 1 month before the study and the duration of the study
- Previously known diagnosis of sleep apnea without ownership of a continuous positive airway pressure (C-PAP) device or agreement to use owned CPAP device during the nights spent in the tent
- Presence of sleep apnea following a positive home sleep test (HST), or have unsafe oxyhemoglobin saturation levels (less than 78%) during a one night sleep monitoring assessment conducted at the Louisiana Sleep Foundation without ownership of a continuous positive airway pressure (C-PAP) device or agreement to use owned C-PAP device during the nights spent in the tent
- History of high altitude sickness
- History of altitude sickness
- Does not have access to a bed or sleeping surface equivalent to or smaller than a Queen size mattress.

RECRUITMENT

Potential participants will be recruited through the PBRC website, e-mails, flyer distribution, and word-of-mouth. Individuals will call or e-mail the Recruitment Core at PBRC and will undergo a phone screen to answer a series of yes or no questions regarding their age, gender, body weight and height, changes in body weight during the last month, presence of disease, and smoking status. Eligible individuals will be scheduled for their screening visit at the PBRC Outpatient Clinic.

SCREENING

Participants will report to the PBRC clinic after a >10-h overnight fast. The screening visit includes an explanation of the purpose of the study, a description of the procedures and the reading and signing of informed consent. Volunteers will then complete a brief personal and family medical history. Height, weight, waist and hip circumference, vital signs (blood pressure, pulse, oral temperature) will be measured. Volunteers will then have an EKG. Subjects with a previous sleep apnea diagnosis must possess a C-PAP device and must agree to use the CPAP device during the nights spent in the tent; if no C-PAP device is available for usage, the subject will not be eligible to participate in the study. If subjects are considered to be eligible up to this point, blood will be drawn for a complete blood count, blood chemistry (Chem15), and a hemoglobin A1-C as part of the draw. Subjects who do not meet the eligibility criteria will be immediately informed in person or by phone. An interview with a trained psychologist will identify potential barriers to enrollment into the SLEEPDIABETES study and also barriers to have the hypoxia tent system setup at the participant's home. Only subjects without a previous sleep apnea diagnosis and who meet all eligibility criteria will next undergo a two-step process to: (1) confirm the absence of sleep apnea (home sleep test, or HST), as well as (2) confirm these subjects without a sleep apnea diagnosis exhibit safe oxygen saturation levels (monitored sleeping study at the Louisiana Sleep Foundation, a certified sleep laboratory) while sleeping under the mild hypoxic conditions denoted by the study. Subjects previously diagnosed with sleep apnea and who possess a C-PAP device will not undergo testing at the Louisiana Sleep Foundation.

(1) Home Sleep Test (HST): Subjects without a sleep apnea diagnosis will first undergo a home sleep test conducted by the Louisiana Sleep Foundation under the direction of [name], MD, DABSM, the chief medical director of the Foundation. Subjects will obtain the home sleep test from [name] and will be given instructions on how to wear the device during a single night of sleep. The device will record breathing rates and oxygen saturation levels throughout the single night of sleep. After the single night sleep, subjects will be instructed to return the device to the Louisiana Sleep Foundation where [name] will review the sleep data and identify the potential presence of sleep apnea. If the presence of sleep apnea is detected, subjects will be immediately informed of their ineligibility to participate in the study. If a negative test for sleep apnea is concluded, subjects will next undergo a monitored sleep study.

(2) Monitored Sleep Study: Subjects who have a negative test for sleep apnea following a HST will next undergo a monitored night of sleep under hypoxic conditions at the Louisiana Sleep Foundation. Subjects will arrive at the Louisiana Sleep Foundation on the evening of their monitored sleep study. A sleep technician will closely monitor the subject's oxyhemoglobin saturation throughout a single night of sleep under hypoxic conditions (2400 m altitude). Hypoxic conditions will be achieved via a hypoxic tent, as previously described and conducted at Pennington Biomedical Research Center [20]. Following the technician-monitored night of sleep, [name] will review the sleep data and provide insight as to the subject's ability to participate in the study given expected oxyhemoglobin saturation levels at 2400 m. Subjects

who exhibit <78% oxyhemoglobin saturations, or who display sleep data of safety concern to [name], will be informed of their ineligibility to participate in the study.

If the HST and sleep center monitoring are within safe ranges for study participation following evaluation by [name], the participant will officially be accepted into the study and will begin baseline testing (Day 0) within weeks and in agreement with schedules. All subjects who have a known sleep apnea diagnosis, possess a C-PAP device, and are agreeable to using the C-PAP device during the nights spent in the tent will be accepted into the study as well.

EXPERIMENTAL DESIGN

This study includes outpatient and in-home visits and will consist of three periods:

- 1) **Baseline** measures of glucose tolerance (OGTT) and body composition (DXA)
- 2) **Intervention** involving 14 night stays in simulated altitude (hypoxic tent in home)
- 3) **Post-treatment** (after 14 nights in hypoxia) measures of glucose tolerance

After screening, subjects will be asked to maintain their usual diet and physical activity levels.

Baseline:

A 75-g OGTT will be performed. Body composition will be measured by DXA. Fasting plasma fructosamine will also be collected via blood draw. A urine pregnancy test will be performed on all females of child-bearing potential prior to the DXA.

Intervention: Nightly exposure to hypoxia

Over the following 14 nights, participants will sleep under a tent simulating an altitude of 2400m (~7500 ft) for 7-12 hrs each night depending on their usual sleep pattern in their bedroom. Each participant will be informed that their partner or household member, or any other individuals, are prohibited from entering or sleeping in the tent.

Post treatment measurements:

After the 7th night of hypoxic sleep, participants will come to the Pennington Biomedical clinic to provide a fasting blood sample to measure glucose and insulin. We will also collect information of the quality of their sleep under the hypoxic tent.

The morning of the 14th exposure to hypoxia, participants will come to the Pennington Biomedical clinic facilities in a fasting state to perform a post intervention assessment.

Approximately 15 min after arrival, a 75-g OGTT will be performed. Fasting plasma fructosamine and hemoglobin A1-C will also be collected via blood draw.

Table 1. Schedule of Procedures

	Screening	Sleep Screening (HST & Sleep Study)	Baseline (Day 0)	Mid-Intervention (Day 7)	Post-Intervention (Day 14)
Health questionnaire	X				
Body weight	X		X	X	X
Vital signs*	X				
Electrocardiogram	X				
Blood draw	X		X	X	X
Oral glucose tolerance test			X		X
Body composition by DXA			X		
Urinalysis	X				
Urine Pregnancy Test			X		
Oxyhemoglobin saturation**		X			

* blood pressure, pulse, oral temperature

** Only performed on subjects without previous sleep apnea diagnosis. Time between screening and sleep screening, as well as sleep screening and baseline testing (Day 0), will vary depending on scheduling at Pennington Biomedical and the Louisiana Sleep Foundation.

METHODS AND PROCEDURES

Urine and blood.

At screening, 9.5ml of blood will be collected for CBC, Chem15 panel, and hemoglobin A1-C analysis. Urine will also be collected at screening for urinalysis. Approximately 39.5 mL of blood will be taken at baseline, and 41.5 mL of blood will be taken at post-intervention for the OGTT, fructosamine, and hemoglobin A1-C analysis. Archives (~10 mL; serum and plasma) will be collected at baseline, mid-intervention, and post-intervention for future analysis. Following the 7th night spent in the hypoxic tent, ~2 ml of blood will be drawn for plasma glucose and insulin concentrations. A total of approximately 122.5 mL (approx. 8.5 Tbl.) of blood will be taken.

Vital signs

Vital signs will be measured while the subject lying on a bed. Body temperature (sublingual) will be measured using an electronic thermometer (Sure Temp 679, Welch Allyn) and blood pressure using a manometer (Baumanometer. W.A. Baum Co., Inc. USA). Heart rate will be measured by radial arterial pulse for 60 seconds.

Overnight exposure to hypoxia (simulated altitude)

Pennington staff will visit the participant's home and setup the hypoxic tent system. This person will also instruct participants on how to use the equipment. Participants will spend 14 consecutive nights in the "altitude tent", with the simulated altitude being set at 2400m over sea-level. Hypoxia will be obtained by nitrogen dilution of the ambient air in an airtight tent (Hypoxico Inc., NY). Briefly, ambient air is filtered and a small part of the oxygen removed before the modified air is flushed in the airtight tent. Altitude is mimicked by lowering the oxygen content rather than reducing the atmospheric pressure. However the physiological stimulus is comparable and has been used in multiple studies involving different populations. This altitude corresponds approximately to the altitude of most mountain resorts and of Mexico City, one of

PBRC# 2015-018

the largest metropolises in the world. It has been chosen because it is within the range of the altitudes eliciting a physiological response to hypoxia, and has been proven to be safe in obese patients during a 1-week exposure [11].

Oral glucose tolerance test

Glucose tolerance will be assessed using an oral 75 g oral glucose tolerance test (OGTT). Subjects will be studied after an overnight fast. An intravenous line will be placed and one baseline sample will be drawn at -5 minutes. The subjects will then consume a 75 g glucose beverage within 5 minutes. Blood samples will be collected at 30, 60, 90, and 120 to measure serum glucose, insulin, and free fatty acid concentrations. Whole body insulin sensitivity will be calculated using the Matsuda insulin sensitivity index ($10,000/\sqrt{[\text{fasting glucose} \times \text{fasting insulin}] \times [\text{mean OGTT glucose} \times \text{mean OGTT insulin}]}$). We will also assess insulin secretion as described by [name]. In brief, the early insulin response during the OGTT, also known as the insulinogenic index is calculated as the ratio of the change in insulin to the change in glucose concentrations from 0 to 30 minutes. The oral disposition index (D_{lo}), a measure of b-cell function is calculated as $[\Delta \text{ insulin}_{0-30\text{min}} / \Delta \text{ glucose}_{0-30\text{min}}] \times 1/\text{fasting insulin}$. Complementary to the glucose response, we would also monitor the changes in the blood FFAs as a measure of the adipose tissue capability to suppress lipolysis in response to insulin. So, it can be used as a marker of insulin sensitivity in terms of adipose tissue. We will calculate the insulin sensitivity index for blood FFAs by the formula: ISI (ffa) = $2/(INSp \times FFAp) + 1$, where INSp and FFAp indicate insulinemic and blood FFA areas, respectively, of the person under study recorded during the OGTT.

DXA scan

Dual X-Ray absorptiometry (DXA) scans will be performed using the GE iDXA whole-body scanner to assess body composition. The protocol requires that participants lie on a table wearing a hospital gown and no metal containing objects, while the scanner emits low energy X-rays and a detector passes along the body. The scan takes 10 minutes and the radiation dose is less than 1 mrem, equal to about 12 hours of background radiation. Fat mass is calculated from weight (kg) on a scale and % body fat and fat-free mass by subtracting fat mass from total body weight (kg).

Sample size. This is a pilot study to test the impact of mild hypoxia in participants with type 2 diabetes. We therefore did not perform a power analysis.

Data analysis

Data will be expressed as mean +/- SE. Values before and after exposure to hypoxia will be compared using the paired Student's t test or a Wilcoxon rank signed test. Despite the pilot nature of this study, the results may be published as a short communication depending on the potential changes in insulin sensitivity.

Data collection, storage and confidentiality

All results will be kept in locked file cabinets and restricted-access computers. All of these will be kept separate from records with names and other personal information. The only people who

PBRC# 2015-018

will know that these patients are research participants are members of the research team. No information about them, or provided by them during the research, will be disclosed to others without their written permission, except if it is necessary to protect their rights or welfare (for example, in case of injury or emergency care), or if it is required by law. When the results of the research are published or discussed in conferences, no information will be included that would reveal the identity of these patients. Participants will be identified by codes when the data gathered in this procedure is presented or published. Authorized representatives of the National Institutes of Health may need to review records of individual participants. As a result, they may see their name; but they are bound by rules of confidentiality not to reveal the patients' identity to others.

RISK/BENEFIT ASSESSMENT

The known risks, inconveniences or side effects involved in this study are the following:

Procedure	Risk
EKG	There are no risks associated with this test. There is a small possibility there may be some redness or irritation if you happen to be allergic to the adhesive on the electrodes.
Body composition by DXA	The amount of radiation used for this procedure is very small. The radiation dose for this scan is equivalent to the radiation you are naturally exposed to in the environment in less than one day. Scans will not be performed on any subject who is pregnant, and all females should inform the DXA technologist if there is any possibility that they are pregnant.
Blood Draws	Bruising, bleeding, pain, infection. These will be minimized by using trained phlebotomists with sterile techniques.

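### The primary endpoint is an open, unranked list of OGTT measures for a single hypothesis; one of them, glucose AUC, should be named as primary before the data are analysed

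*Combined protocol and SAP*

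**What the plan says.** All references are to the combined protocol and SAP.

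- **HYPOTHESIS AND AIMS.** There is one directional hypothesis: two weeks of nightly hypoxia "in obese, type 2 diabetic subjects will improve glucose tolerance". The primary endpoint reads "Primary endpoint: Results from the 75 g oral glucose tolerance test (OGTT) assessed by different statistical approaches including", followed by glucose and insulin AUC, a repeated-measures mixed model, the Matsuda index and a "calculation of indices of insulin sensitivity and insulin secretion". The items are not ranked. Fructosamine, HbA1c and body weight form a separate exploratory tier.
- **SUBJECTS.** "We plan to have n = 10 completers".
- **Oral glucose tolerance test.** "Whole body insulin sensitivity will be calculated using the Matsuda insulin sensitivity index". The early insulin response is "also known as the insulinogenic index is calculated as the ratio of the change in insulin to the change in glucose concentrations" over the first 30 minutes. An oral disposition index, described as a measure of beta-cell function, and a free-fatty-acid sensitivity index are added.
- **Sample size.** "This is a pilot study to test the impact of mild hypoxia in participants with type 2 diabetes". No power analysis was done.
- **Data analysis.** Before and after values are compared by a paired t test or a Wilcoxon signed-rank test, with no rule for choosing between them. Alpha and sidedness are not given, and the mixed model is not mentioned. Publication as a short communication is foreseen, depending on what happens to insulin sensitivity.

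**The concern.** The listed items are not one result computed in several ways. Glucose AUC, or a mixed model of glucose, measures glucose tolerance directly. The plan itself describes Matsuda as insulin sensitivity and the disposition index as beta-cell function. For insulin AUC and the insulinogenic index it does not say which direction would be favourable. AUC is not specified as total or incremental, and the outcome of the mixed model is not named.

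If insulin sensitivity rose while glucose AUC stayed flat, the plan gives no way to decide whether the hypothesis was supported. A favourable change in one index could then be presented as the primary result and read as better glucose tolerance. Linking publication to insulin sensitivity, which is not the quantity in the hypothesis, makes that selective emphasis easier.

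**Working it through.** The plan has no figure to reproduce, since it states no alpha, effect size or power. The question is how often at least one measure would show a significant improvement when nothing has changed, **if** any one measure could count.

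**Inputs from the plan:** 10 completers, paired comparison (9 df), and the listed measures.

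**Assumed, because the plan gives none:** two-sided 5% per measure, the correlations, the OGTT curves, and what counts as improvement. Improvement is coded as lower glucose AUC, lower insulin AUC, and higher Matsuda, insulinogenic and disposition indices.

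**Step 1. One measure.** 0.05 / 2 = 2.5% in the favourable direction.

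**Step 2. Limits for several measures.** If independent, the chance is 1 − 0.975^k.
- k = 2: 1 − 0.975² = 4.9%
- k = 3: 1 − 0.975³ = 7.3%
- k = 5: 1 − 0.975⁵ = 11.9%
- Ceiling for five under any correlation: 5 × 2.5% = 12.5%

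**Step 3. Five equally correlated measures.** Paired t tests, n = 10, 200,000 simulated trials per value:

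| Correlation | 0 | 0.3 | 0.5 | 0.6 | 0.7 | 0.8 | 0.9 | 0.95 |
|---|---|---|---|---|---|---|---|---|
| Any false improvement | 11.9% | 10.8% | 9.7% | 8.9% | 7.9% | 6.8% | 5.5% | 4.4% |

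**Step 4. Simulated OGTT curves.** All measures come from the same samples, so their correlations follow from the curves. Assumed mean glucose is 150/215/265/275/255 mg/dl and mean insulin 15/45/70/80/75 at 0/30/60/90/120 minutes. Day-to-day variation for glucose is 3-6% per point plus 6% shared, and for insulin 8-20% per point plus 15% shared. The glucose-insulin correlation is 0-0.6. Between-subject log-SD is 0.15 for glucose and 0.5 for insulin. Six settings, 40,000 trials each:

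| Measures that could count | Any false improvement |
|---|---|
| Glucose AUC and Matsuda | 3.8-4.4% |
| Plus disposition index | 5.8-6.2% |
| Plus insulinogenic index | 6.9-7.5% |
| Plus insulin AUC (five) | 8.2-8.8% |

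A set closer to the list under HYPOTHESIS AND AIMS (both AUCs, Matsuda, insulinogenic index, and 1/fasting insulin as a stand-in for the sensitivity index) gave 7.5-8.6% in a separate simulation with different curve inputs and four settings.

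**Step 5. Does glucose AUC support the false claim?** In the five-measure case, glucose AUC is itself not significantly improved in 70-73% of the false improvements.

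**Step 6. Choice of test.** If the t or Wilcoxon test may be chosen after seeing the data, the five-measure rate is 10.6-11.0%, against 2.7-2.9% for glucose AUC alone.

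**Step 7. One primary or an adjustment?** For a mean change of 1 SD of the paired differences at n = 10, power from the noncentral t is 80.3% at 0.05 and 50.4% at 0.05 / 5 = 0.01.

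**The case against.** The strongest objection is that these rates need a rule the plan does not contain. A reader might infer that the trial will claim success on any one favourable measure, or that its false-positive rate is already 8-9%. The documents do not support either. They describe one test assessed in several ways, which can fairly be read as a plan to report everything side by side. This stands, and the percentages are only conditional. What remains is that the plan does not exclude selecting one measure and does not say how a mixed pattern would be judged.

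Second, the five-measure figure depends on directions that the plan does not assign to insulin AUC and the insulinogenic index. The two codings tend to pull against each other, which raises the total. The disposition index is also not in the list under HYPOTHESIS AND AIMS. This stands too, so the 4% for glucose AUC and Matsuda must be read beside the 8-9%. The figure near 12% needs five uncorrelated measures, which is implausible when all come from the same samples.

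Third, this is an unpowered pilot with ten completers, and strict multiplicity control is arguable. That lowers the weight of the point but does not remove it. The plan states a hypothesis, says the pilot is to test the impact of hypoxia, uses significance tests, and separates primary from exploratory endpoints.

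Fourth, a reader might infer that one named primary guarantees a 2.5% false-improvement rate. It does not. The design is an uncontrolled before-after comparison, and any drift between visits would move glucose AUC as well.

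**Conclusion.** The point holds in a limited form. The primary endpoint is open and unranked, its items measure different things, and the plan has no lead measure, success rule, alpha, multiplicity rule or rule for choosing the test. A favourable change in one index with glucose AUC unchanged could be presented as the primary result.

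If any one measure could count, the chance of a false improvement runs from about 4% (glucose AUC and Matsuda) to about 8-9% (five measures), with about 12% as the uncorrelated extreme, against 2.5% for one. These figures rest on an assumed two-sided 5%, assumed correlations and curve inputs, directions assigned in this review, and no drift between visits. They show what the wording permits and are not an error rate of the stated plan.

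This is a cheap improvement, modest in weight because the study is an unpowered pilot.

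**What to change.** Before the data are analysed:

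1. Name the Day 0 to Day 14 change in glucose AUC 0-120 as the single primary endpoint, and state total or incremental in advance. Total is a reasonable default because it keeps changes in fasting glucose.
2. Test it with a two-sided paired t test at 0.05, with Wilcoxon as a sensitivity analysis. Report the mean paired change with its 95% CI.
3. Label insulin AUC, Matsuda, the sensitivity and secretion indices and the mixed model as secondary and unadjusted.
4. Commit to reporting the primary result whatever insulin sensitivity does.

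One named primary is preferable to a Bonferroni split over five measures, given the power loss shown above.

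The title page gives a latest IRB approval in September 2017 and an upload date in October 2019, so results may already exist. If the data have been seen, label the choice of primary as post hoc and report all listed measures together.

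The cost is a wording amendment, since every sample needed is already planned. The downside is that a significant secondary index can no longer be presented as confirming the hypothesis.

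### For participants with diagnosed sleep apnea, safety in the tent rests on C-PAP being worn and working, and no stated procedure records either

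*Combined protocol and SAP*

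**What the plan says.** **Rationale.** The section on reasons for the protocol modification separates two sources of hypoxia. It reports that the FDA was not worried by the tent's own level, but that "there was concern that safety would be compromised if the hypoxia of sleep apnea was added to the hypoxia of the tent". At first the safeguard was to exclude people with apnea. The modification admits them on C-PAP, on the ground that a device drawing tent air "would also insure that additional hypoxia would not occur due to the C-PAP eliminating the sleep apnea". It then says of participants without apnea and those treated with C-PAP: "Both of these groups of patients will be protected from any additional hypoxia associated with sleep apnea".

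**Eligibility.** The inclusion criterion for this group is a known diagnosis and "ownership of a continuous positive airway pressure (C-PAP) device that must be worn throughout the nights spent in the tent". SCREENING accepts those who have the diagnosis, possess the device and agree to use it in the tent. It then adds: "Subjects previously diagnosed with sleep apnea and who possess a C-PAP device will not undergo testing at the Louisiana Sleep Foundation". The Table 1 footnote limits the saturation measurement in the same way.

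**During the tent nights.** RISK/BENEFIT ASSESSMENT repeats that C-PAP must be used. Its row on sleeping under hypoxia gives C-PAP wear as the reason no risk is expected in this group. At Day 7 the staff ask about sleep quality. Adverse events are checked at Day 7 and Day 14 and through calls between visits. The Data Safety Monitoring Plan makes investigators responsible for protocol compliance.

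**Analysis.** Values before and after hypoxia are compared within person by a paired t test or Wilcoxon test.

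**The concern.** The rationale is written for people whose apnea is under control on C-PAP, but the criteria ask only for a diagnosis, a device and an agreement. Control is never checked, and wear is required without a stated way of knowing whether it happened. A participant whose device is left off, or does not control the apnea, would be exposed to the combined hypoxia that the protocol names as its safety concern. That person could still complete all 14 nights.

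There is a second, smaller stake in the result. Oral diabetes treatment is held constant, with "no change in the treatment for 1 month before the study and the duration of the study". No matching rule covers C-PAP, while the tent period makes nightly use compulsory. A person who used the device irregularly before Day 0 and every night afterwards would have two changes at once, and the data would not show it.

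**Working it through.** The plan gives no figure to reproduce here; it sets 10 completers without a power analysis. The check is a comparison of the text for the two groups, followed by short arithmetic.

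**Step 1. What each group goes through** (SUBJECTS, SCREENING, Table 1, RISK/BENEFIT ASSESSMENT)

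| Item | No apnea diagnosis | Diagnosed, owns C-PAP |
|---|---|---|
| General criteria, EKG, blood tests, psychologist interview | yes | yes |
| Home sleep test | yes, must be negative | no |
| Monitored saturation night at 2400 m | yes, must be safe | no |
| C-PAP worn on tent nights | not applicable | required |
| Record of C-PAP wear | not applicable | none stated |
| Evidence that C-PAP controls the apnea | not applicable | none stated |
| Saturation on the home tent nights | none stated | none stated |

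SCREENING gives the two sleep tests different purposes. The home test looks for apnea, and the laboratory night looks at saturation in the tent. A known diagnosis makes the first redundant. Omitting the second relies on the premise that C-PAP removes the apnea.

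**Step 2. Could another provision supply the record?** Table 1 has no C-PAP item. That is weak evidence by itself, because Table 1 also omits the Day 7 sleep enquiry and the adverse event checks, which are planned in the text. The text was therefore searched as well. It describes no device log, diary, adherence question, residual apnea measure or oximetry on C-PAP. The sleep enquiry concerns quality, the adverse event checks depend on symptoms or events, and the compliance duty is general.

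**Step 3. Exposure per C-PAP user** (EXPERIMENTAL DESIGN: 14 nights, 7 to 12 hours each)

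- Whole intervention: 14 × 7 = 98 h to 14 × 12 = 168 h.
- Before the Day 7 visit: 7 × 7 = 49 h to 7 × 12 = 84 h.
- Still ahead after that visit: 98 − 49 = 49 h to 168 − 84 = 84 h.

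The Day 7 visit follows the seventh night, so a record reviewed there can be acted on before night 8.

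**Step 4. What cancels in the paired comparison.** For person *i*, write the OGTT change as H + C + error. H is the effect of the tent and C is the effect of any change in C-PAP use between the two periods. Apnea equally present in both periods largely subtracts out. If use does not change, C = 0. If it does, the mean change over *n* completers, of whom *m* are C-PAP users, shifts by (m/n) × (mean C among users). The documents give neither *m* nor C, so no value is put on this term.

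**The case against.** The strongest reply is that the exemption is deliberate and reasoned. C-PAP is the standard treatment, wear is mandatory, and identified staff must ensure compliance. Participants still pass the cardiac, pulmonary and altitude-sickness exclusions, the EKG and the interview on barriers to having the tent at home. Symptoms are monitored and acute altitude sickness leads to withdrawal. All of this stands. Responsibility for compliance is assigned; what is missing is the method and the data for it to work on.

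A reader might infer that these participants are enrolled on three conditions and nothing else. That is wrong: the three conditions are the only *sleep-specific* ones. A reader might also infer that C-PAP use will go wholly unrecorded or that non-use could never be noticed. The documents show only that no recording procedure is stated. The Day 7 conversation could bring non-use to light, and the consent pages are not available to check.

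The FDA's non-significant-risk letter might also be cited. It is dated June 2015 and answers an April 2015 submission, whereas the modification cites over a year of enrolment limited to people without apnea. The available documents do not show that the letter covered C-PAP users. Nor do they show any FDA objection to them.

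**Conclusion.** The point holds as a gap in verification. For the group the modification admits, protection against added apnea hypoxia depends on C-PAP wear and effectiveness over 98 to 168 hours per person, and no stated procedure records either. This assumes only the stated 14 nights of 7 to 12 hours. The number of C-PAP users, their adherence and their residual apnea are not given, and none is assumed.

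Three stronger readings are not supported:

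- **That the OGTT result is biased.** Stable apnea largely cancels, and a change in C-PAP use is a possibility of unknown size and direction. What can be said is that, without use data, a reader of this uncontrolled pilot cannot tell whether such a change occurred.
- **That most of the sample is affected, from the 86% apnea prevalence the protocol cites.** Prevalence in overweight and obese people with diabetes is not the share of enrolled participants who are diagnosed and own a device.
- **That C-PAP users must spend the laboratory night.** That would test saturation on C-PAP once. It would not verify wear at home, and it would slow recruitment in a study that enrolled one patient in over a year.

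This is an inexpensive improvement that the study should make.

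**What to change.** 1. **Table 1.** Add a row, *C-PAP use (C-PAP users only)*, at Day 0, Day 7 and Day 14. Record nights and hours worn from the device log, with the residual apnea index where the device reports it. Where there is no log, use a diary issued at screening, covering the 14 nights before Day 0 and continued through the tent nights.
2. **RISK/BENEFIT ASSESSMENT, safety monitoring.** The medical investigator reviews the Day 0 record before night 1 and the Day 7 record before night 8. Tent exposure is withheld or stopped for a night without C-PAP, or for sustained non-use beyond a threshold fixed in advance. Brief mask removal should not count. The documents offer no figure for the threshold, so the medical investigator should set it before the first C-PAP user starts.
3. **Data analysis.** List each C-PAP user's use before and during the tent nights beside that person's OGTT change. No additional test is needed.

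**Cost.** No new visit is needed. C-PAP users bring the device, log or diary to existing visits, and those without a log receive a diary at screening. The main downside is that a non-adherent participant may need replacing to reach 10 completers.

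**Limit.** A diary is self-reported and cannot show whether the device controls the apnea, so the log is preferable where one exists.
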